5.6 SECUNDARY ANALYSIS

5.6.1 Efficacy

- To demonstrate the ability of PulmoVista 500 to visualize regional ventilation changes, a quantitative evaluation is performed by calculating the cross-correlation coefficients between the impedance waveforms of PulmoVista 500 and the ventilator volume waveforms of OLV patients. The evaluation is carried out as in the primary analysis.
- In addition, a qualitative evaluation of the regional changes will be carried out. To do so, three blinded raters compare the corresponding sections of all OLV patients independently. Based on the information from the PulmoVista 500 video sequence provided, the raters evaluate which of the two halves of the lung is ventilated. The results are entered patient-related (pseudo-patient number) in the following table by the rater:

Pseudo-Patnr.	Valuation	
1	1	
2	2	
3	0	
4	1	
.	.	

Description of valuation:	0	not assessable
	1	right ventilated / left blocked
	2	left ventilated / right blocked

Tab. 1: Example of table for the qualitative evaluation of the OLV patients and the associated rating

The PulmoVista 500 video sequences to be assessed are created according to a workflow (see Appendix 7.3 Workflow for the creation of OLV videos) and made available to the raters. The pseudo-patient numbers are randomly generated by lot. These three tables of the raters will be merged into the KKS. A decision is considered positive or negative if at least two raters have come to the same result. In the opinion of one or more raters, is it not possible to judge the waveform (Code 0), the following assignment applies:

1x not evaluable & 2x same decision -> clear assignment in the table,
 1x not assessable & unequal decision of the remaining 2 raters -> drop out,
 2x or 3x not evaluable -> drop out.

A 2x2 Table will be created in the following form from the 3 tables of the raters (one of each rater):

Reference	Evaluation of the raters (with information provided by PulmoVista 500)	
	right ventilated / left blocked	left ventilated / right blocked
right ventilated / left blocked	a	b
left ventilated / right blocked	c	d

Tab. 2: Table for the accordance of rater and reality of the OLV patients

From this table, the success rate $(a + d) / (a + b + c + d)$, the sensitivity $a / (a + b)$, the specificity $d / (c + d)$ and the corresponding confidence intervals are calculated. The reverence (real side of the ventilation) is taken in the study documentation (e.g. Name of corresponding Marker and/or MACRO Database) of the individual patients.

- To assess the ability of PulmoVista 500 to display changes in ventilation-induced tidal volumes through the "Trend View", the plausibility questionnaire across all patients is evaluated. The questions of the plausibility questionnaire in relation to the "main view" are individually counted according to their categories (yes / no / n.a.) and listed as a percentage.
- To assess the ability of PulmoVista 500 to display changes in end-expiratory lung volumes (induced by e.g. PEEP changes, recruitment and suction maneuvers) using the "dELLI Trend View", the plausibility questionnaire is evaluated across all patients. The questions of the plausibility questionnaire in relation to the "dELLI trend view" are individually counted according to their categories (yes / no / n.a.) and listed as a percentage.
- The evaluation of clinical usefulness, the nine questions of the questionnaire on clinical usefulness, are individually counted according to their category level (1 very difficult ... to ... 5 very useful) and listed on a percentage basis. Furthermore, the mean and standard deviation are calculated for each of these nine questions.

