6.1.3 PRIMARY AND SECONDARY STUDY ENDPOINTS

PRIMARY STUDY ENDPOINT

The capability of PulmoVista 500 for continuous monitoring of ventilation and its changes at different points in time during varying states of regional ventilation, the cross-correlation function (CCF) between global tidal impedance (EIT) waveforms and global tidal volume (ventilator) curves will be evaluated.

SECONDARY STUDY ENDPOINTS

- First secondary endpoint: To assess the capability of PulmoVista 500 to detect changes in regional ventilation by evaluating the cross correlation between impedance waveforms derived from PulmoVista 500 and volume curves derived from ventilator during one-lung-ventilation.
- Assess that changes of tidal volumes induced by ventilator settings can be monitored by the "Trends view"
- Assess that changes of the end-expiratory lung volumes (induced by e.g. PEEP changes, recruitment and suctioning maneuvers) can be monitored by "dELLI trend view"

- Documentation of any safety events related to the use of PulmoVista 500
- Assessing the use specific clinical helpfulness of PulmoVista 500 - clinical helpfulness of PulmoVista 500 is proven if
 - see attachments (chapter 23.1) clinical usability

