3.3 SECUNDARY STUDY OBJECTIVES

3.3.1 Efficacy

- To demonstrate the ability of PulmoVista 500 to display regional ventilation changes, a quantitative evaluation is performed using the cross-correlation coefficient between the impedance waveforms of PulmoVista 500 and the ventilator volume waveforms in the subgroup of OLV patients.
- To evaluate Pulmo Vista 500's monitoring features, it assesses whether changes in tidal volumes induced by ventilation settings are represented by the "main view". For this purpose, the plausibility questionnaire is evaluated.

- Assess that changes of the end-expiratory lung volumes (induced by e.g. PEEP changes, recruitment and suctioning maneuvers) can be monitored by “dEELI trend view”. The plausibility questionnaire is also evaluated for this.
- To evaluate the clinical usefulness of PulmoVista 500, the questionnaire on clinical utility across all patients is evaluated.
- In order to demonstrate the ability of PulmoVista 500 to produce controlled induced regional changes, an evaluation is performed using the OLV subgroup. Three blinded rater evaluate the corresponding waveforms.

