5.5 PRIMARY ANALYSIS

The basic data for the analysis is recorded in a database. The ventilation data for both waveforms- the global impedance waveforms and the volume waveforms- are stored for each patient in a cloud and prepared using a statistical analysis algorithm (see Appendix 7.2 Workflow for determining the time ranges used to calculate the cross correlation between the global impedance waveform (PulmoVista 500) and the volumetric waveform (Evita V500)).

The two EXCEL tables per patient contain the two waveforms to be compared (Appendix 7.2, Section 14, Columns A, B, C and N). From this, two cross-correlation coefficients per patient were calculated. The cross-correlation coefficients are a measure of the relationship between the two waveforms.

Figure 1 shows a section of both waveforms unstandardized. The numbers and diagrams are examples from the study „Assessment of the capability of PulmoVista 500 to

continuously monitor regional ventilation distribution and its changes over time",
Investigation reference number PulmoVista 500-30022.

[figure not shown]

Fig. 1: PulmoVista 500 Impedance Waveform (Global- blue) and Reference Volume Waveform (RTD_Vol_mL- green) unstandardized over time

If you standardize both waveforms, you get the following figure:

[figure not shown]

Fig. 2: PulmoVista 500 Impedance Waveform (Global- blue) and Reference Volume Waveform (RTD_Vol_mL- green) standardized over time

Figure 2 shows a slight time shift of the waveforms to each other.

In this example there is e.g. a correlation coefficient (Pearson) of 0.871 for the waveforms. Taking into account the shift (here Lag = 10: Shift from one curve to the other by 10 measuring times in both directions from 0) it results in a cross-correlation coefficient of 0.995.

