7 APPENDIX

7.1 REFERENCE VALUES OF LABORATORY PARAMETERS

[figure not shown]
Omitted

7.2 WORKFLOW FOR DETERMINING THE TIME RANGES USED TO CALCULATE THE CROSS CORRELATION BETWEEN THE GLOBAL IMPEDANCE WAVEFORM (PULMOVISTA 500) AND THE VOLUMETRIC WAVEFORM (EVITA V500).

Workflow for determining the time ranges used to calculate the cross correlation between the global impedance waveform (PULMO VISTA 500) and the volume waveform (EVITA V500)

[figure not shown]
Step Description

- 1 Open EIT Data Analysis Tool SW 6.1
- 2 Use the **Load** button to load the first file in the series containing the intervention to be evaluated; the beginning and the type of intervention are marked by an event marker (see example below)
- 3 Use the button **Sequence to ...** to load the last file of the series containing the intervention to be evaluated
- 4 Record the total length of the loaded files (time scale below ROI 4)

[figure not shown]
5 Select the files (1 min each) that lie directly before (1) or after (2) the intervention, in which a uniform impedance waveform, and in particular no artifacts, can be seen and in which no parts of the intervention itself are contained.

Example: series of 10 files per 1 min, in which the interventions took place between min 3 and 4.

[figure not shown]

6 Place cursor in the area of file 1 (exact position does not matter, in this example within the third minute)

- 7 Use the buttons **Display ...**, **Time scale** to set the time scale to 60 sec

- 8 Use the button **File ..., save as ASC** to convert the selected file 1 as ASCII file
(the created ASC file is saved in the same directory with the same file name as the selected EIT file, and a two-digit, incremental counter is added to the file name)
- 9 Use the Buttons **Display ...**, **Time scale** to increase the time scale so that the recorded total length is displayed again.
- 10 Place cursor in the area of file 2 (exact position does not matter, in this example within the 5th minute)
- 11 Use the buttons **Display ...**, **Time scale** to set the time scale to 60 sec

- 12 Use the button **File ..., Save as ASC** to convert the selected file 2 as ASCII file
- 13 Now open the two generated ASC files with the statistical evaluation software
- 14 In the area below the line (Image; Time; Global;), Determine the cross-correlation between column C (Global) and column N (~ Volume [ml]).

97	A	B	C	D	E	F	G	H	I	J	K	L	M	N

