7.7 EVALUATION ROUTINES

Example of the calculation of the cross correlation coefficients: (in the example the maximum cross-correlation coefficient is **CCF=0.984** by a lag-shift of 8)

```
GET DATA
  /TYPE=XLSX
  /FILE='U:\Verz_Studien\PULMOVISTA\XXX\XXX_prae.xlsx'
  /SHEET=name 'Tabelle1'
  /CELLRANGE=FULL
  /READNAMES=ON
  /DATATYPEMIN PERCENTAGE=95.0
  /HIDDEN IGNORE=YES.
EXECUTE.
DATASET NAME DataSet1 WINDOW=FRONT.

SAVE TRANSLATE OUTFILE='U:\Verz_Studien\PULMOVISTA\XXX\XXX_prae.xlsx'
  /TYPE=XLS
  /VERSION=12
  /MAP
  /FIELDNAMES VALUE=NAMES
  /CELLS=VALUES
  /REPLACE.

Data written to U:\Verz_Studien\PULMOVISTA\XXX\XXX_prae.xlsx'.
4 variables and 3000 cases written to range: SPSS.
Variable: Image          Type: Number    Width:  5    Dec: 0
Variable: Time           Type: Number    Width: 12    Dec:10
Variable: Global          Type: Number    Width: 18    Dec:13
Variable: RTDVol.mL       Type: Number    Width: 19    Dec:15

SAVE OUTFILE='U:\Verz_Studien\PULMOVISTA\XXX\XXX_prae.sav'
  /COMPRESSED.
DATASET ACTIVATE DataSet1.
CCF
  /VARIABLES=Global RTDVol.mL
  /NOLOG /MXCROSS 15.
```

CCF

[DataSet1] U:\Verz_Studien\PULMOVISTA\XXX\XXX_prae.sav

Model Description

Model Name	MOD_1	
Series Name	1	Global
	2	RTDVol.mL RTD: Vol. [mL]
Transformation	None	
Non-Seasonal Differencing	0	
Seasonal Differencing	0	
Length of Seasonal Period	No periodicity	
Range of Lags	From	-15
	To	15
Display and Plot	All lags	

Applying the model specifications from MOD_1

Case Processing Summary

Series Length	3000
Number of Excluded Cases	User-Missing Value
Due to	System-Missing Value
Number of Valid Cases	3000
Number of Computable Zero-Order Correlations After	3000
Differencing	

Global with RTDVol.mL RTD: Vol. [mL]

Cross Correlations

Series Pair: Global with RTDVol.mL

RTD: Vol. [mL]

Cross		
Lag	Correlation	Std. Error ^a
-15	,687	,018
-14	,710	,018
-13	,732	,018
-12	,754	,018
-11	,774	,018
-10	,794	,018
-9	,813	,018
-8	,831	,018
-7	,848	,018
-6	,865	,018
-5	,880	,018
-4	,895	,018
-3	,909	,018
-2	,921	,018
-1	,933	,018
0	,943	,018
1	,953	,018
2	,961	,018
3	,968	,018
4	,974	,018
5	,978	,018
6	,981	,018
7	,983	,018
8	,984	,018
9	,983	,018
10	,981	,018
11	,977	,018
12	,972	,018
13	,966	,018
14	,958	,018
15	,949	,018

a. Based on the assumption that the series are not cross correlated and that one of the series is white noise.

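### The OLV cross-correlation is presented as evidence on regional ventilation, but it uses the Global impedance signal, which carries no information on which lung is ventilated

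*SAP*

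**What the plan says.** **Purpose.** Protocol 6.1.3, repeated in the synopsis, states: "First secondary endpoint: To assess the capability of PulmoVista 500 to detect changes in regional ventilation by evaluating the cross correlation", with OLV as the setting. SAP 3.3.1 takes this over for the OLV subgroup: "To demonstrate the ability of PulmoVista 500 to display regional ventilation changes, a quantitative evaluation is performed using the cross-correlation coefficient". SAP 5.6.1 opens its first bullet in the same way: "To demonstrate the ability of PulmoVista 500 to visualize regional ventilation changes".

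**Method.** SAP 5.6.1 gives one instruction for this analysis: "The evaluation is carried out as in the primary analysis". The primary analysis is defined in three places:

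- SAP 5.5: "The two EXCEL tables per patient contain the two waveforms to be compared (Appendix 7.2, Section 14, Columns A, B, C and N", that is, image number, time, Global and volume.
- SAP Appendix 7.2, step 14: "Determine the cross-correlation between column C (Global) and column N (~ Volume [ml".
- SAP Appendix 7.7, the SPSS call: "VARIABLES=Global RTDVol.mL", with lags from -15 to +15.

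SAP 5.5 then averages each patient's pre and post coefficients and tests the mean against zero with a one-sample t-test at a level of 0.05.

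**The other OLV analysis.** The second bullet of SAP 5.6.1 has three blinded raters state from a video which lung is ventilated. Their majority answer is set against the documented side in a 2x2 table, with success rate, sensitivity, specificity and confidence intervals. Protocol 7.2 states the secondary hypothesis as telling normal from single-lung ventilation and detecting presence or absence of ventilation in each lung. It also calls for a 2x2 table.

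**The concern.** The endpoint concerns where ventilation goes. The signals named for it are whole-plane impedance and total delivered volume, and neither has a left or right. The example export in Appendix 7.2 contains four regional columns (Local 1 to Local 4), but no step of the quantitative analysis uses them.

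The risk lies in reporting. A high OLV coefficient could be presented as showing regional capability when it shows only that the global curve follows the ventilator, which the primary analysis already addresses in the same patients. This matters because Protocol 3.2 says the data are needed for authorization in other countries, and attachment 23.2 calls the plausibility of the regional information one of the study's major purposes.

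**Working it through.** **1. Is Global the sum of the regions?** Inputs: the 14 data rows printed in SAP Appendix 7.2 (sheet rows 99 to 112). Formula: S = Local 1 + Local 2 + Local 3 + Local 4, compared with Global. Row 103 in full: 282.248383 + 1402.36475 + 1634.34448 + 161.750122 = 3480.707735, against a printed Global of 3480.70776.

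| Sheet row | Sum of Locals | Global as printed |
|---|---|---|
| 103 | 3480.70773 | 3480.70776 |
| 105 | 3519.15401 | 3519.15405 |
| 107 | 3604.16613 | 3604.16602 |
| 109 | 3737.58014 | 3737.58008 |
| 111 | 3910.58847 | 3910.58862 |

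These five rows agree to within 0.0002. Row 110 differs by 0.01. Seven rows (99, 100, 101, 102, 106, 108, 112) differ by 1, 5 or 10 to within 0.0002, the pattern that a single misread digit leaves. Row 104 prints Global as 349.09839 against a sum of 3494.19848, so a digit has been lost. Misreading is an inference, but no row points to another relation.

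**2. What follows for the coefficient.** Write G = L1 + L2 + L3 + L4 and let V be ventilator volume. Suppose the device assigns the same signal to the wrong regions, giving L1' to L4' with the same sum at each time point. Then G' = G, the correlation of G' with V equals that of G with V at every lag, and so does the maximum over lags -15 to +15. This holds whether the Locals are quadrants or layers, and whichever minutes are chosen.

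**3. Illustration.** Assumptions: a 3000-sample record with an invented breath shape, a fixed total impedance change and fixed noise.

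| Device shows | Global CCF | Right-half CCF | Left-half CCF |
|---|---|---|---|
| Correct lung (right) | 0.9975 | 0.998 | 0.010 |
| Wrong lung (left) | 0.9975 | 0.023 | 0.998 |
| 50/50 split | 0.9975 | 0.996 | 0.996 |

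The first column is constant by construction, so it adds no evidence to step 2. The table shows only that half-lung curves separate states that Global cannot.

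**4. If the total does change.** With signal SD s and independent noise SD n, r = s / √(s² + n²). Take r = 0.92 as an assumed start: s²/n² = 0.8464 / 0.1536 = 5.51. Halving the amplitude gives 5.51 / 4 = 1.378, and r = √(1.378 / 2.378) = 0.76. The coefficient can therefore move between two-lung and one-lung ventilation, but a halved amplitude gives 0.76 whichever lung produced it.

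**5. Averaging.** The patient value is (CCF pre + CCF post) / 2. Pre 0.9 with post 0.7, pre 0.7 with post 0.9, and 0.8 twice all give 0.8. Any before/after contrast, even a non-regional one, is lost before the test.

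**6. What the rater table covers.** Its codes are right ventilated, left ventilated and not assessable. Under Appendix 7.3 the video runs between markers set before and after OLV is induced, so raters may see the change, but the form has no code for two-lung ventilation. The table tests the side. It does not quantify the normal versus single-lung contrast in Protocol 7.2.

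**The case against.** The strongest reply is that the regional question is tested elsewhere. The blinded rating uses a documented reference, yields proportions with confidence intervals and can fail. It is also the analysis closest to the protocol's secondary hypothesis: Protocol 7.2 asks for a 2x2 table, and Protocol 7.1 bases the 22 patients (25 enrolled) on a difference in proportion, not on a mean coefficient. Plausibility question 2 in attachment 23.2 also asks whether the image shows the blocked side correctly. All of this stands. A reader might infer that the regional objective has no test able to fail; the documents do not support that.

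A second reply is that the OLV bullets say impedance waveforms without the word global, so the cross-reference might carry over only the statistical steps. That is possible, but no regional signal is named anywhere for this analysis, and the three definitions of the primary analysis all name Global.

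A third concerns scope. A reader might infer that the coefficient must stay the same when ventilation moves from two lungs to one. That needs the total impedance signal to be preserved, and the documents do not show this. Protocol 2.4 says EIT sees one cross-sectional plane, and amplitude or shape may differ between the states. Step 4 shows that such a change alters the coefficient without making it regional.

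**Conclusion.** As specified, the OLV cross-correlation cannot answer the question set for it. Given the total signal, its sensitivity to location is zero, and it repeats the primary analysis in about 25 of the 80 patients. This rests on reading the instruction in SAP 5.6.1 as including the signals of the primary analysis, and on Global being the sum of the Locals, which the cleanly printed rows show.

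The point is limited to this analysis. The primary endpoint is unaffected, and the ventilated side is tested by the raters. What remains is a secondary endpoint whose label claims more than its method can deliver, and a normal versus single-lung contrast that neither OLV efficacy analysis in SAP 5.6.1 quantifies. Protocol 7.3 sets no pass/fail criterion, so the harm would be in interpretation. It should be fixed, but it does not undermine the trial.

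**What to change.** **Wording, at almost no cost.** In SAP 3.3.1 and 5.6.1, call the OLV cross-correlation a description of global signal agreement during OLV and remove the statement that it demonstrates regional capability. State that the claim about the ventilated side rests on the blinded-rater 2x2 table. Record the difference from Protocol 6.1.3, as Protocol 7.6 requires.

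**Addition, if left and right curves can be exported from the stored EIT recordings.** For each OLV patient, compute the right-lung share of tidal impedance variation, right / (right + left), in the recorded two-lung, right-only and left-only phases. Report the within-patient change from two-lung ventilation to each single-lung phase with its 95% confidence interval, and the number of patients whose share moves in the documented direction. Protocol 6.4.2.2 already has these phases recorded and each step marked. Its request for one minute per side is worded for the double lumen tube, so report how many patients have each phase.

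**Cost.** Re-processing for about 25 patients, with no new patients, visits or measurements. The SAP describes no left/right export and does not say what areas Local 1 to 4 cover, so feasibility must be confirmed first. The directional count will partly overlap with the 2x2 success rate; the new information is the two-lung comparison.

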7.2 STATISTICAL DESIGN

Null-Hypothesis

The PulmoVista 500 is not capable of continuously monitoring ventilation.

Primary Endpoint (Efficacy)

To assess the capability of PulmoVista 500 for continuous monitoring of ventilation and its changes at different points in time during varying states of regional ventilation, the cross-correlation function (CCF) between global tidal impedance (EIT) waveforms and global tidal volume (ventilator) curves will be evaluated.

- To refute the null-hypothesis of this trial it must be shown that the global tidal impedance waveforms and the global tidal volume curves correlate

⁷ Fischer E, Gremse F. Assessment of the capability of PulmoVista® 500 to continuously monitor regional ventilation distribution and its changes over time. An Animal Study. FINAL STUDY REPORT. PulmoVista 500-30022. Aix Scientifics. 2016-01-27

significantly, i.e. that the correlation scores are significantly different from zero.

- If the null-hypothesis is refuted the capability of PulmoVista 500 is assumed to be a valuable diagnostic device for long-term monitoring of mechanical ventilation.

The mean value of the intra-subject cross-correlation function (CCF) between global impedance (EIT) waveforms and global volume (ventilator) curves will be determined.

Secondary Endpoint (Efficacy)

To assess the capability of PulmoVista 500 to detect regional changes of ventilation it shall be tested, whether EIT can correctly differentiate between normal and single-lung ventilation.

- To refute the null-hypothesis of this trial it must be shown that the regional information about tidal impedance variation matches the clinical changes from normal to single-lung ventilation, i.e. that EIT detects ventilation vs. no ventilation in each lung.
- If the null-hypothesis is refuted the capability of PulmoVista 500 is assumed to be a valuable diagnostic device for detecting regional ventilation changes during long-term monitoring of mechanical ventilation.

The diagnostic output of the EIT measurements will be compared with clinical ventilation settings in a 2x2 table.

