7.3 WORKFLOW FOR THE CREATION OF OLV VIDEOS

This workflow describes the creation of the video sequences which are used to assess the capability of PULMO VISTA 500 to monitor regional changes during mechanical ventilation within the OLV-subgroup.

Software:

- Dräger EIT Simulation Tool
- Camtasia Recorder 8
- Camtasia Studio 8

Workflow:

1. Identify the acquisition dates and the patient/site IDs of all OLV patients
2. Identify relevant markers which are set prior and post the induction of one lung ventilation
 - a. document time-stamp of each marker
3. Load EIT-data into *Dräger EIT Simulation Tool*
 - a. Select the “Folder” which contains the acquisition date
 - b. Select the “Subfolder” which contains the relevant patient ID (xx_yyy)
 - c. Select the start-“File” which includes the relating “PRE-Marker”
 - d. Select the “Sequence to file” which includes the relating “POST-Marker”
4. Start *Camtasia Recorder 8*
5. Adjust the recording window according to the size of the “Main”-view
6. Start the simulation within *Dräger EIT Simulation Tool*
7. Start the recording
8. After the simulation has completed one entire loop of simulation, stop the recording
9. Save the recorded video file (use site and patient ID, as well as date of recording) for the definition of the file name
10. Load recorded video file into *Camtasia Studio 8*
11. Crop video sequence according to the previously identified time-stamps of the pre and post markers (the video sequence now contains only the EIT information between the two markers)
12. Process the final video sequence as MP4-file
13. Save the MP4-file containing the respective site and patient ID as well as the date of video processing.

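### The blinded OLV rating takes no verdict on two-lung ventilation and has no code for a readable display that wrongly shows both lungs ventilated

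*SAP*

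**What the plan says.** For the OLV secondary endpoint, Protocol 7.2 states that "it shall be tested, whether EIT can correctly differentiate between normal and single-lung ventilation". It explains its criterion as showing that "EIT detects ventilation vs. no ventilation in each lung", and adds: "The diagnostic output of the EIT measurements will be compared with clinical ventilation settings in a 2x2 table". Protocol 6.4.2.2 provides the data. Both states are measured between induction and surgery. The physician is asked for a baseline of at least 2 minutes after intubation and for at least 1 minute with each lumen of the double-lumen tube clamped. Each step of the placement test is marked in the device.

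In SAP 5.6.1 three blinded raters see a video, and "the raters evaluate which of the two halves of the lung is ventilated". Each rater enters one value per pseudo-patient number: 1 (right lung ventilated, left blocked), 2 (the reverse) or 0 (not assessable). Two matching verdicts decide. Otherwise the rules are "1x not assessable & unequal decision of the remaining 2 raters -> drop out" and "2x or 3x not evaluable -> drop out". Tab. 2 crosses the reference with the raters' verdict, and on both axes the only categories are the two single-lung states. On the reference: "The reverence (real side of the ventilation) is taken in the study documentation". The success rate is (a+d)/(a+b+c+d), with a/(a+b) called sensitivity and d/(c+d) specificity.

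SAP 7.3 defines the clip: "Identify relevant markers which are set prior and post the induction of one lung ventilation", then crop to the stretch between them.

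Separately, question 2 of the plausibility questionnaire (Protocol 23.2) asks, with one lung blocked, whether the Tidal Image shows the correct non-ventilated side. SAP 5.6.1 tallies the answers as yes, no or n.a.

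**The concern.** Telling normal from single-lung ventilation requires verdicts in both states. The rating takes them only for clips of OLV, and its answer sheet implies that one lung is blocked. It therefore cannot show how often the display suggests a blocked lung when none is blocked.

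The second gap lies within OLV. A display that clearly but wrongly shows both lungs ventilated is a failure of the kind Protocol 7.2 asks about. It is neither right nor left, and it is not unassessable. Without a coding instruction, the same failure may count as an error, count as correct or drop out, depending on how the raters cope with the missing code.

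Protocol 7.2 ties a favourable conclusion about the device's diagnostic value to this test, and Protocol 3.2 says that the study is to provide data for authorization in other countries. A success rate that can lose failures from its denominator is a weak basis for either.

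**Working it through.** **1. The plan's own figure.** Protocol 7.1 gives 22 evaluable OLV patients (two-sided alpha 0.05, power 0.9, difference 0.1 in a proportion) and 25 enrolled. It states no baseline proportion. If reference agreement is taken as 100% and tested against 90%, a single failure rejects, and power is 1 − 0.9^22 = 0.902, so 22 is reproduced. A baseline of 99% against 89% would need 47. On the reading that reproduces 22, every wrong display must count as a failure. Suppose the true failure rate is 10% and half of the failures leave the count. The power to see one is then 1 − 0.95^22 = 0.68.

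**2. Question against data.**

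| | Protocol 7.2 | SAP 5.6.1 |
|---|---|---|
| States compared | normal vs single-lung | right vs left, during OLV |
| Verdict on a two-lung phase | needed | none |
| Meaning of a/(a+b), d/(c+d) | – | correct side named, for each side |
| Wrong both-lungs display in OLV | failure | no code |

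The number of two-lung verdicts planned is 0. One baseline clip per patient with no false indication would give an exact upper 95% limit of 13.7% (0/25) or 15.4% (0/22).

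**3. Effect of the missing code.** No document gives a frequency for such displays, so k = 4 is an assumption. All other patients are assumed to be rated correctly. The base is the 25 enrolled, because 22 is already net of drop-outs. Intervals are exact (Clopper-Pearson).

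- Counted as errors: (25 − 4)/25 = 21/25 = 84.0% (63.9 to 95.5).
- At least two raters enter 0 for each: 21/21 = 100% (83.9 to 100).
- Every rater picks a side with an even chance: expected (21 + 4 × 0.5)/25 = 23/25 = 92.0%.
- Each rater enters 0 half the time and otherwise picks evenly. Each side then has probability g = 0.25 per rater. The chance of a majority for one given side is 3g²(1 − g) + g³ = 0.1406 + 0.0156 = 15.6%. Each display is thus correct in 15.6%, an error in 15.6% and dropped in 68.75%. The expected reported rate is 97.3%.

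On a base of 22, the four results are 18/22 = 81.8% (59.7 to 94.8), 18/18 = 100% (81.5 to 100), 90.9% and 96.9%.

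**4. Other values of k, base 25.**

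| k | Counted as errors | Picked evenly (expected) | Coded 0 and dropped |
|---|---|---|---|
| 1 | 24/25 = 96% | 98% | 100% |
| 3 | 22/25 = 88% | 94% | 100% |
| 5 | 20/25 = 80% | 90% | 100% |

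**The case against.** - **The failure is recorded elsewhere.** Plausibility question 2 is asked in exactly the state where this failure occurs, and a both-lungs display would be answered no. That stands: a reader might infer that the failure goes unrecorded throughout the study, and the documents do not support this. But the question is not put to the blinded raters, is answered only if routine allows, does not enter the success rate and says nothing about two-lung phases. Questions 1 and 6 concern regions already known to be poorly ventilated or removed.
- **The Protocol's criterion is largely met.** Codes 1 and 2 each make a statement about both lungs, and the clip may show the transition. This also stands in part, so it would be wrong to say that the SAP ignores Protocol 7.2. What is missing is a verdict when both lungs are ventilated.
- **Code 0 has defined consequences.** It does, and drop-outs can be seen by comparing a+b+c+d with the 25 planned. What is undefined is whether a readable but wrong display belongs under code 0. The total would not separate it from a missing or unreadable clip.
- **The reference might be thought ambiguous where both sides were tested.** No mis-scoring follows, because each clip is scored against its own marker. Only the choice of clip is open.
- **The numbers are hypothetical.** They are. Independent, evenly guessing raters are also an assumption, and errors on a shared clip would probably be correlated. The range in step 3 from 84.0% to 100% does not depend on that assumption; the expected values of the mixed case do.
- **This is a secondary, qualitative analysis with no pass/fail criterion** (Protocol 7.3). True, but Protocol 7.1 and 7.2 give the OLV endpoint its own sample size and null hypothesis.

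**Conclusion.** The point holds in a limited form and should be fixed. The blinded rating tests whether the correct side is named during OLV. It covers the normal versus single-lung question only in part and yields no rate of false blocked-lung indications during two-lung ventilation. Within this rating, a readable but wrong both-lungs display has no code and may leave the denominator, so the success rate can be too high.

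The size is unknown. With 4 such displays in 25, the same data could be reported anywhere from 84.0% to 100%, assuming that all other ratings are correct. This shows the direction and possible reach of the problem. It does not predict that such displays will occur, and the documents give no ground for saying that the reported rate will in fact be inflated. Confidence is high for the missing verdict and the missing code.

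**What to change.** Amend SAP 5.6.1 and 7.3:

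- (a) Add a code for both lungs ventilated. Count a majority for it during OLV as an error.
- (b) Have the same three raters also judge, in random order, the recorded two-lung baseline and whichever clamped or blocked phases are available, using the existing markers. Keep the planned transition clip. Fix in advance which marker pair defines each clip and which side the transition clip shows.
- (c) Report a 2x2 table of state (normal, single-lung) against majority verdict (both lungs, one lung), with confidence intervals that allow for several clips per patient. Label the present a/(a+b) and d/(c+d) as correct-side rates.
- (d) Report how many clips have a code-0 majority or no majority, including three-way splits. Give the success rate with these excluded and with them counted as not correct.

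Cost: SAP wording and rating time, with no new patient procedure. Two extra clips in 22 patients make 44, and three in 25 make 75. That is 132 to 225 ratings over three raters, or about 0.7 to 1.3 hours of video per rater at 1 minute per clip. The number falls where a phase was not recorded: the recording times are requests to the physician, and the clamping request names only double-lumen tubes. Reported accuracy may come out lower. A lung already poorly ventilated at baseline may score as a false indication, so such cases should be listed.
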